3. * Explain what actions or procedures research personnel should take to inform the PI of such a discovery :

No additional actions will be taken if participants do disclose substance use.

4. * Will findings be disclosed to participants and/or any other person/group outside of the study team?

Yes
 No

5. If pertinent and/or incidental findings will not be disclosed, explain why not:

Because the research is centered around women in recovery from substance use disorder and being conducted in clinics where these women are receiving care for their substance use disorder, there is not a necessity to take any action if participants do disclose substance use.

Risk Benefit Complete

Protocol Progress:

- **INITIAL SETUP**
- **BACKGROUND, RATIONALE & GOALS**
- **RESEARCH PLAN**
- **CONSENT PLAN**
- **RISKS, PRIVACY & CONFIDENTIALITY**
- ⑥ **POPULATIONS WITH SPECIAL CONSIDERATIONS**
- ⑦ **INSTITUTIONAL REQUIREMENTS**
- ⑧ **DOCUMENTS**

Click Continue below to go to the next section

Populations with Special Considerations

1. * Check all participant groups that will be either

a) Specifically included in this study or

b) Discernable in the research data/specimens.

(Selections will branch)

Children

Emancipated minors

Wards of the State

Pregnant women or fetuses

Neonates or Post-delivery Materials

Prisoners

Decisionally Impaired Adults

VCU / VCUHS students or trainees

VCU / VCU Health System employees

Individuals with limited English proficiency

Active military personnel

Student populations in K-12 educational settings or other learning environments

Members of a federally recognized American Indian and Alaska Native tribe

None of the Above

2. * Check all of the following categories that apply to this research:

45 CFR 46.204 Research involving pregnant women or fetuses.

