View Follow up visit scripts	Project BETTER Follow-up Visits Script.docx	0.01	10/11/2021 [name]	7:36 PM Study reminders/communications	Yes
View [name] CV	CEM_CV_08.15.21_BT.pdf	0.01	10/10/2021 [name]	9:23 PM CV/Biosketch	Yes
View [name] CV	[name] CV .pdf	0.01	10/10/2021 [name]	5:44 PM CV/Biosketch	Not Applicable

Study Population

1. * Provide the maximum number of individuals that

1. May participate in any study interaction or intervention (Including screening, consenting, and study activities)

AND/OR

2. You obtain any data/specimens about (regardless of identifiability)

at VCU and at other sites under the VCU IRB's oversight. See the help text for additional guidance.

70

2. If this is a multi-Center Project, what is the maximum anticipated number of subjects across all sites?

N/A

3. * Provide justification for the sample size by explaining how you arrived at the expected number of participants and why this number is adequate for answering the research questions:

Target sample size: N=30 (15 per study condition)

As this is a pilot feasibility trial, 30 study participants is the recommended sample size (Browne, 1995).

Browne R.H. (1995) On the use of a pilot sample for sample size determination. Statistics in Medicine 14, 1933–1940.

Based on our prior experience, we anticipate about 20% of eligible participants we approach will not be interested in the study, which will be about 10.

Additionally, we will abstract information from the medical record on the birth hospitalization for participants' infants, which includes an additional 30.

This makes a total of 70 as above.

4. * List the study inclusion criteria:

- 1) Female
- 2) ≥18 years of age
- 3) Meet criteria for Opioid Use Disorder
- 4) Currently receiving MOUD pharmacotherapy (including buprenorphine, buprenorphine/naloxone, or methadone)
- 5) Pregnant (<34 weeks EGA)
- 6) Engaged in treatment at OB MOTIVATE for ≤10 weeks during the current pregnancy OR engaged in community-based OUD treatment for ≤10 weeks during the current pregnancy

5. * List the study exclusion criteria:

- 1) Considering/planning adoption
- 2) Present with a serious cognitive/psychiatric impairment
- 3) Existing language barriers making true informed consent impossible

6. Justify the inclusion and exclusion criteria if you are either targeting, or excluding, a particular segment of the population / community. Provide a description of the group/organization/community and provide a rationale.

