5. * Describe the study procedures/methods for identifying and recruiting participants. Address all of the following three aspects of recruitment in your response.

1. Identification of potentially eligible participants or secondary data/specimens of interest.

- What database(s) will be queried to identify secondary data/specimens
- How VCU Informatics or VCU IRDS will be used for cohort identification (when applicable, see help text)
- How potential participants' contact information will be obtained

2. Recruitment procedures to invite participation in the study (when applicable):

- How each of the written or verbal recruitment materials and reminders (selected above) will be used
- Who will contact, approach, or respond to potential participants
- Locations where recruitment procedures will take place
- The timing and frequency of recruitment attempts

3. Eligibility screening prior to consent and how those activities will be carried out (when applicable)

See the help text for additional guidance.

1. We will recruit pregnant women in treatment with the VCU OB MOTIVATE program. The OB MOTIVATE program sees pregnant, postpartum, and parenting women for substance use disorder treatment no matter if they plan to or delivered at VCU with no time limitation for treatment continuation, making our program a growing referral provider for surrounding OBGYN and behavioral health practices. OB MOTIVATE currently sees approximately 70 pregnant and postpartum/parenting women for at least one outpatient encounter each month between our two VCU locations (Nelson/AOP Women's Health and MOTIVATE Addiction Medicine clinics). The OB MOTIVATE at Nelson/AOP clinic schedule and the medical record will be accessed by the research assistant to assess potential eligibility (18 or older, pregnant, <34 weeks gestation, receiving MOUD, engaged in treatment at OB MOTIVATE for ≤10 weeks during the current pregnancy) in order to identify which potential participants to approach about the study.

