3. Following consent, participants will complete the first study visit, a baseline assessment (electronic survey & brief RA questions). Then participants will be randomized (1:1) to either the technology-based modules (intervention) group or the brochure (control) group. Randomization and intervention introduction can be completed at the same time of the other first study visit procedures (ie, pre-survey) or as a supplemental unpaid visit based on participant preference (ie, if the participant wants to complete the pre-survey remotely and the intervention introduction in person). Participants will be provided access via email/text to the modules or the electronic brochure (based on randomization) for three weeks. Following the 3-week study intervention period, participants will complete two follow-up study visits (electronic survey & brief RA questions): 1) during pregnancy within two weeks of intervention timeframe (Study visit 2) and 2) within 4-8 weeks postpartum (Study visit 3). Enrolled, randomized participants not completing Study visit 2 within 5 weeks of study condition introduction, but wishing to do so, will be reviewed by the PI on a case-by-case basis for the opportunity of continued study participation. Specifically, if the participant is no longer pregnant, study continuation will not be allowed; if still pregnant, the PI will consider the option of study continuation (e.g., completion of follow-up visit 1) for the participant. For each study visit, we will also obtain health information (as per secondary data page and uploaded document) via the health record after participants have agreed to the HIPAA authorization in the consent form. Participants will be compensated \$20 per study visit (up to \$60 total).

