- c. See chart abstraction forms (attached) for information to be abstracted from the medical record at each study visit.

**Community-based addiction treatment:

No secondary data will be obtained. All data will be self-reported by the participant via survey and interview questions.

2. * Describe whether any agreement exists between you and data/specimen provider that states you will never have access to the ability to identify the participants (i.e. access to identifiers or the code key) and that you will not attempt to re-identify individuals.

Each participant's StudyID will be linked to their medical record number to allow other study visit data to be linked to the protocoled medical record abstraction. This information will be kept in a separate key file within the secure RedCap database. The key linking the Study ID to the participant medical record ID will be destroyed upon completion of the study.

3. * When the information/specimens were originally collected, did individuals provide consent for secondary research use of their data/specimens (i.e. consent to another research study or to a research registry)?

Yes

No

Costs to Participants

1. * Select all categories of costs that participants or their insurance companies will be responsible for:

- Participants will have no costs associated with this study
- Study related procedures that would be done under standard of care
- Study related procedures not associated with standard of care
- Administration of drugs / devices
- Study drugs or devices
- Other

Compensation

It is recommended that investigators consult with [VCU Procurement Services](#) before proposing a compensation plan (monetary or non-monetary) to the IRB to ensure the plan will comply with VCU policies. Refer to [WPP XVII-2](#) for the IRB's guidelines about compensating research participants.

1. * Describe any compensation that will be provided including:

- 1. total monetary amount**
- 2. type (e.g., gift card, research pre-paid card, cash, check, merchandise, drawing, extra class credit)**
- 3. how it will be disbursed**
- 4. how you arrived at this amount**
- 5. What identifiers and tax forms will be required for compensation purposes (i.e. W-9 form, SSN, V#, addresses, etc.)**

Participants will receive \$20 for each of the three study visits. Total possible compensation is \$60.

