- The information or specimens were/will be obtained under a waiver of informed consent, waiver of HIPAA authorization, or an exempt study that did not use an information sheet.
- Other reason why anonymous use/sharing is not inconsistent with the consent document

7. * The Principal Investigator certifies that prior to releasing an anonymized dataset or anonymized specimens the following conditions will all be met:

- all 18 HIPAA identifiers (including all dates) will be removed;
- all indirectly identifiable data elements (unusual, rare, uncommon data) will be removed, grouped, suppressed, or otherwise transformed to no longer be readily identifiable;
- a different subject ID will be assigned than the one used for the main study and a linkage key will not be kept; and
- the PI will review the dataset/specimens to confirm that the remaining information could not be used alone or in combination with any other information to re-identify the participants represented in the data.

See *help text for more information.*

- Yes
- No

8. * The Principal Investigator certifies that after the study has been closed with the VCU IRB, the following conditions will be met whenever individual level research information and/or specimens are used or shared:

- The identities of participants who are represented in the dataset/specimens will not be readily ascertainable or otherwise re-identifiable by the recipient;
- If a linkage/code key is created, it will be maintained at VCU and not shared with the recipient under any circumstances;
- The PI will have no knowledge that the remaining information could be used alone or in combination with any other information to identify the individuals represented in the data; and
- The PI agrees to abide by this sharing plan even after the study has been closed with the VCU IRB.

- Yes
- No
- N/A - No sharing will occur

Pertinent Results and Incidental Findings

1. * Is it likely investigators could discover a participant's previously unknown condition (e.g. pregnancy, disease, suicidal thoughts, wrong paternity, genetic results, or other findings that may be of importance to health or well-being) or if a participant is engaging in illegal or reportable activities:

Yes
 No

2. * Describe what possible pertinent results or incidental findings stemming from research-only procedures may be discovered.

The RA-led questions at each study visit ask about substance use which may include use of illicit substances.

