45 CFR
46.205(d) **Research involving viable neonates.**

45 CFR 46.206 Research involving, after delivery, the placenta, the dead fetus, or fetal material.

45 CFR 46.207 Research not otherwise approvable which presents an opportunity to understand, prevent, or alleviate a serious problem affecting the health or welfare of pregnant women, fetuses, or neonates.

Children

1. * Check all that apply to the study:

45 CFR 46.404 Research involving no greater than minimal risk to children, with adequate provisions for soliciting the assent of the children and permission of their parents or guardians, as set forth in Sec. 46.408

45 CFR 46.405 Research involving greater than minimal risk but presenting the prospect of direct benefit to individual participants

45 CFR 46.406 Research involving greater than minimal risk and no prospect of direct benefit to individual participants, but likely to yield generalizable knowledge about the participant's disorder or condition

45 CFR 46.407 Research not otherwise approvable which presents an opportunity to understand, prevent or alleviate a serious problem affecting the health or welfare of children. (Research in this category must be reviewed and approved by the Secretary of the Department of Health & Human Services)

2. If multiple categories are selected above, explain which study groups are covered by each selected category (e.g. treatment vs. control groups):

N/A

3. * Describe how you plan to obtain permission of parents or legal guardians. If you have indicated this study will fall into categories 406 or 407, please describe here how you will obtain permission from both parents.

Pregnant females will be consented and enrolled in this study. For OB MOTIVATE patients, consent will include chart abstraction of information about their babies after birth

4. * Describe how children will be assented to participate in the study (i.e. what will the study team do during the assent process to ensure the child understands what the research involves).

We will not be including children, just abstracting data about newborn health right after birth for OB MOTIVATE patients.

Pregnant Women or Fetuses

1. * When scientifically appropriate, briefly describe any preclinical studies (including studies on pregnant animals) and clinical studies (including studies on nonpregnant women) that have provided data for assessing potential risks to pregnant women and fetuses [45 CFR 46.204(a)].
N/A

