View [name] CV	CEM_CV_08.15.21_BT.pdf	0.01	10/10/2021	[name]	CV/Biosketch	Yes
			9:23 PM			
View [name] CV	[name] CV .pdf	0.01	10/10/2021	[name]	CV/Biosketch	Not Applicable
			5:44 PM			

HIPAA

In order for VCUHS to meet HIPAA regulations regarding accounting of disclosures, data retention, and data destruction requirements for PHI data obtained without patient authorization, members of the study team (including principal investigators) are directed to consult with VCU Informatics to obtain any VCUHS data. This does not include obtaining data for which the study team has patient authorization. [VCU Health System Authority and Affiliates Policy COMP-014]

For data requests, including preparatory to research and research with decedents, submit a request for the desired PHI, or for a consultation on alternate methods to obtain the data, at <https://informatics.vcu.edu>.

HIPAA Privacy Board Requirements

For guidance, see <https://www.vcuhealth.org/our-story/who-we-are/compliance-services/compliance-services>

1. * Select the source of the Individually Identifiable Health Information. See help text for definitions.

- PHI associated with or derived from (i.e. obtained from or entered into) VCU Health medical records or VCU Dental Care records
- Research Health Information (RHI) created or received by a study and kept solely in study records (e.g. self reported or the result of research tests and not entered into health records)
- PHI associated with or derived from (i.e. obtained from or entered into) a non-VCU HIPAA covered entity's health records

2. * Summarize the types of health information that will be obtained or used in this research. Do not describe only the identifiers that you will collect or use during the study.

For OB MOTIVATE patients: Medical record data will be abstracted for each participant including physician notes (e.g., substance use and treatment history) and test results (e.g., urine drug testing). All medical record chart abstraction items are included in the attached chart abstraction forms. Each participant's study ID will be linked with patient identifiers in a key kept in a secure database to facilitate this data abstraction.

Phone numbers and email addresses will be used to contact participants to schedule and complete study visits.

Community-based addiction treatment: All health information will be self-reported by participants using surveys and RA-led questions.

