3. * Describe the source(s) of the protected health information (e.g. Informatics or which clinical databases):

OB MOTIVATE patients: The source will be VCU Cerner/EPIC electronic medical record.

Community-based addiction treatment: Participant self report

4. * Does the PI certify that this study's access to and use of the protected health information is limited to the minimum amount necessary to be able to effectively conduct the research?

Yes No

5. * Select all pathways this research will employ to use or access PHI (selections will branch):

- De-Identified Data (none of the 18 identifiers are recorded or associated with the research data)
- Limited Data Set
- Waiver of Authorization
- Partial Waiver of Authorization (temporary waiver for recruitment purposes and/or waiver of some elements of Authorization)
- Signed Authorization Combined with Consent Form
- Signed Authorization as Stand-Alone Form

Partial Waiver of Authorization

1. * Select the purpose for requesting the partial waiver of authorization:

- Identify possible participants to recruit for the study
- Waive some elements of authorization (such as signature)

2. * If you selected "Waive some elements of authorization" above, list the elements you want to waive (see the help text) and explain why:

Signatures are requesting to be waived to facilitate remote study procedures, such as consent, and to utilize IRB approved REDCap e-consent procedures. A signature will be obtained from participants recruited and completing research procedures in person.

3. * Explain how the partial waiver of authorization poses no greater than minimal risk to participants' privacy:

(Alternative question phrasing: How do the risk(s) of this use of identifiable health information compare to the risks to privacy a person might reasonably experience in normal everyday life?).

Regarding waiving the signature, participants are provided with all other elements of HIPAA authorization in their informed consent process, and their PHI remains protected as described in the authorization, regardless of whether a signature is obtained.

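### Do chart-derived variables need a rule of their own because they exist only for OB MOTIVATE participants?

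*Combined protocol and SAP*

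**What the plan says.** Two recruitment streams feed one trial of 30 participants, 15 per arm (Study Population Q3 and Q4). All participants have the same three visits, each with an electronic survey and brief questions from the research assistant (Study Procedures Q7, item 3).

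The medical record comes on top of that, for one stream only:

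- Community stream: "No secondary data will be obtained. All data will be self-reported by the participant via survey and interview questions" (Secondary Data/Specimen Details Q1).
- OB MOTIVATE stream: "The source will be VCU Cerner/EPIC electronic medical record" (HIPAA Q3). The items include "physician notes (e.g., substance use and treatment history) and test results (e.g., urine drug testing" (HIPAA Q2).
- Infants: the study is "just abstracting data about newborn health right after birth for OB MOTIVATE patients" (Children Q4).

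Three places are worded more broadly. Study Procedures Q7 says: "For each study visit, we will also obtain health information (as per secondary data page and uploaded document) via the health record". Study Population Q3 says "we will abstract information from the medical record on the birth hospitalization" for participants' infants and counts 30 of them. Secondary Data/Specimen Details Q2 links every participant's study ID to a medical record number. In addition, Study Procedures Q5 describes OB MOTIVATE as offering "substance use disorder treatment no matter if they plan to or delivered at VCU".

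**The concern.** A variable that exists only in the chart is absent by design for every community participant. If an analyst treated those blanks as ordinary missing data, or as negative findings, the result would be wrong. A variable built from the chart for some women and from self-report for others would be measured differently by recruitment source. Recovery is the stated exploratory outcome most open to this, since urine drug tests and treatment history could feed it, and the trial collects no specimens that would give community participants an equivalent.

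Infant data carry a second gap. A birth at another hospital may not appear in the VCU record. Place of birth is also settled after randomisation, because women enrol before 34 weeks. Comparing arms only among infants with a VCU record would therefore condition on a post-randomisation event. With 15 per arm at best, losing a good share of records would leave very little precision. The supplied text has no analysis section that says how any of this would be handled.

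**Working it through.** **1. The plan's own figure.** Study Population Q3 gives 30 participants, about 10 people who decline, and 30 infants: 30 + 10 + 30 = 70, as stated. Deriving the decliners from the stated 20% gives 30 / 0.8 = 37.5, so 38 approached and 8 declining, for a total of 68. That agrees with 70, given that the 10 is described as approximate. The infant term equals the full sample, so it was not reduced for community participants or for births elsewhere. Study Population Q1, which this total answers, asks for a maximum.

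**2. How many records could exist.** Let c be the number of community participants and o the share of OB MOTIVATE births not in the VCU record. The documents give neither, so both are assumptions. With singletons and no loss to follow-up:

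- mothers with chart data = 30 − c
- infants with chart data = (30 − c) × (1 − o)

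| c | o | Mothers | Infants | Infants per arm |
|---|---|---|---|---|
| 0 | 0 | 30 | 30 | 15 |
| 6 | 0.2 | 24 | 19.2 | 9.6 |
| 10 | 0.2 | 20 | 16 | 8 |
| 15 | 0.3 | 15 | 10.5 | about 5 |

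Community recruitment is passive, by flyer and QR code, while the research assistant is embedded in the OB MOTIVATE clinic (Study Procedures Q5). Nothing in the text points to the bottom row.

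**3. What that would do to an arm comparison.** For a binary outcome at 50%, the approximate 95% half-width is 1.96 × √(2 × 0.25 / n per arm). At n = 15 it is 1.96 × 0.183 = 0.358, or 36 percentage points. At n = 8 it is 1.96 × 0.25 = 0.49, or 49 points. The normal approximation is rough at these sizes. Both intervals are too wide to support a conclusion about the intervention, and no section plans such a comparison of infants.

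**4. Which stated outcomes use the chart.** The aims (Background, Rationale and Goals Q3; repeated in Study Procedures Q2) name feasibility and acceptability as primary, and mental health, recovery, functioning and quality of life as exploratory. No infant outcome, chart-only outcome or mixed chart and self-report outcome appears. For substance use, the area where chart and self-report overlap most, a common source is at hand: "The RA-led questions at each study visit ask about substance use" (Pertinent Results and Incidental Findings Q2).

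**5. Whether the broad sentences conflict with the narrow ones.** Study Procedures Q7 refers the reader to the secondary data page, which carries the restriction. HIPAA Q2 gives the ID linkage under the OB MOTIVATE heading, and Data Confidentiality and Storage Q9 names the record number only as an example of an identifier. Read together, the sections describe one procedure.

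**6. Bias.** Recruitment source is fixed before randomisation. An arm comparison of maternal chart variables within OB MOTIVATE is therefore a comparison in a subgroup defined at baseline: smaller, but valid. Only infant records raise the post-randomisation question.

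**The case for a change.** The best case for a change is that the text was only partly updated when community recruitment was added. The chart abstraction forms are dated October 2021, and the community recruitment materials October to November 2022. A separate Visit 3 Delivery Questions form also dates from October 2022. If it is the self-report counterpart of the birth chart data, the same item could be charted for some women and self-reported for others. A short list of each variable with its source would prevent that and would cost almost nothing.

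Part of this stands. The infant count and the ID-linkage sentence are looser than the sections on children and HIPAA. Anyone reporting a chart variable should give its denominator by arm and recruitment source, and should not count community participants as missing or negative. An arm comparison restricted to infants with a VCU birth record would need a caution.

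The rest does not carry through to the plan. The operating procedures document, which Study Procedures Q7 names as the place for design and procedures, is not among the supplied text, and neither are the abstraction forms. A list missing here is not shown to be missing from the plan. The Delivery Questions form also means that birth data may exist without a VCU record. Reporting all chart-only variables without an arm comparison would discard the valid baseline-defined comparison in step 6.

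**Conclusion.** No change is called for. Chart-derived data are confined to OB MOTIVATE participants, and the documents say so repeatedly. Chart-abstracted infant data may be thinner still: 30 records if neither gap occurs, 16 with 10 community participants and 20% of births elsewhere, and about 10 under the most pessimistic assumptions tabulated. Those shares are assumptions, and the shortfall affects no outcome that the supplied text names. The figure of 30 infants is part of a declared maximum and is correct as a ceiling. The unrestricted linkage sentence is a wording slip that HIPAA Q2 already resolves.

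The remaining gap, which denominator to print beside a chart variable, is one that analysts fill sensibly in a pilot of this size. This conclusion rests on the exploratory outcomes being scored from the common surveys and research-assistant questions. If the operating procedures define recovery or an infant measure from the chart, the denominator and the post-randomisation caution would apply to that variable alone.
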